10.2 Primary Efficacy Endpoints

There are two primary efficacy endpoints in this clinical investigation. The two primary efficacy endpoints will be based on analyses of CNC word recognition. The objective of the two primary efficacy endpoints is to test for non-inferiority of remote MAP programming via telecommunication compared to live MAP programming.

For each of the two primary endpoints, a one sample t-test will be used to test for treatment effects.

10.2.1 Primary Efficacy Endpoint 1

The objective of the first primary efficacy analysis is to demonstrate non-inferiority of facilitated remote MAP programming via telecommunication compared to traditional audiologist live MAP programming for word recognition in quiet as evaluated with the CNC test. Success for the first primary endpoint will be based on rejection of the null hypothesis of inferiority, with a non-inferiority margin of 10% based on clinical judgment and variability observed in previous studies. The treatment effect will be estimated using a one sample t-test. If the upper limit of the two-sided 95% confidence bound is less than 10, statistical significance will be met at the 0.025 alpha level. The first primary endpoint is represented by the following hypotheses:

$$H_0: CNC_{diff} \geq 10\%$$

$$H_a: CNC_{diff} < 10\%$$

where:

CNC_{diff} = Live Audiologist MAP - Facilitated Remote MAP programming treatment difference for CNC word recognition.

10.2.2 Primary Efficacy Endpoint 2

The objective of the second primary efficacy analysis is to demonstrate non-inferiority of unassisted remote MAP programming via telecommunication compared to traditional audiologist live MAP programming for word recognition in quiet as evaluated with the CNC test. Success for the second primary endpoint will be based on rejection of the null hypothesis of inferiority, with a non-inferiority margin of 10% based on clinical judgment and variability observed in previous studies. The treatment effect will be estimated using a one sample t-test. If the upper limit of the two-sided 95% confidence bound is less than 10, statistical significance will be met at the 0.025 alpha level. The second primary endpoint is represented by the following hypotheses:

$$H_0: CNC_{diff} \geq 10\%$$

$$H_a: CNC_{diff} < 10\%$$

where:

CNC_{diff} = Live Audiologist MAP - Unassisted Remote MAP programming treatment difference for CNC word recognition.

10.3 Secondary Efficacy Endpoint

The objective of the secondary efficacy analysis is to demonstrate non-inferiority of unassisted remote MAP programming via telecommunication compared to facilitated remote MAP programming via telecommunication for word recognition in quiet as evaluated with the CNC test. Success for the second co-primary endpoint will be based on rejection of the null hypothesis of inferiority, with a non-inferiority margin of 10% based on clinical judgment and variability observed in previous studies. The treatment effect will be estimated using a one sample t-test. If the upper limit of the two-sided 95% confidence bound is less than 10, statistical significance will be met at the 0.025 alpha level. The secondary efficacy endpoint is represented by the following hypotheses:

$$H_0: CNC_{diff} \geq 10\%$$

$H_a: CNC_{diff} < 10\%$

where:

CNC_{diff} = Facilitated Remote MAP - Unassisted Remote MAP programming treatment difference for CNC word recognition.

11 TYPE 1 ERROR CONTROL

Study success will be defined by rejection of the null hypotheses in the comparison of facilitated remote MAP programming via telecommunication to live MAP programming and/or the rejection of the null hypothesis in the comparison of unassisted remote MAP programming via telecommunication to live MAP programming for CNC word recognition. Because study success is based on two separate endpoints, type I error will be maintained at an overall one-sided alpha level of 0.025. The secondary efficacy objective will be tested only in the event both co-primary efficacy objectives are met. Thereby preserving the overall 0.025 alpha level

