**Figure 2: Study visit flow chart**

## Endpoint Testing

**Primary Safety Endpoint: Characterize the safety profile of device and/or procedure related adverse events associated with facilitated remote MAP programming, unassisted MAP programming and audiologist live MAP programming**

Safety Endpoint testing will occur at Visit 2 and Visit 4.

- Recipients will be MAPped via telecommunication by a remotely located audiologist.
- Any adverse events associated with the MAPping will be recorded on the New Adverse Event Reporting Form. Any AEs identified at Visit 2 or Visit 4 will be re-evaluated at subsequent visits and updated on the Follow Up Adverse Event Reporting Form.

**Co-Primary Efficacy Endpoint 1: Demonstrate that performance on CNC words using a remotely programmed facilitated MAP is no worse than when using a live programmed MAP**

Efficacy Endpoint 1 testing will occur at Visit 1 and Visit 3.

- **Visit 1:** Speech perception scores will be obtained in Program 1 (familiar/Live)
- **Visit 3:** Speech perception scores will be obtained in Program 2 (Facilitated MAP)

**Co-Primary Efficacy Endpoint 2: Demonstrate that performance on CNC words using an unassisted remotely programmed MAP is no worse than when using a live programmed MAP**

Efficacy Endpoint 2 testing will occur at Visit 1 and Visit 5.

- **Visit 1:** Speech perception scores will be obtained in Program 1 (familiar/Live)
- **Visit 5:** Speech perception scores will be obtained in Program 2 (Self MAP)

**Secondary Efficacy Endpoint: Demonstrate non-inferiority of unassisted remote MAP programming compared to facilitated MAP programming via performance on CNC words.**

Efficacy Endpoint 2 testing will occur at Visit 3 and Visit 5.

- **Visit 3:** Speech perception scores will be obtained in Program 2 (Facilitated MAP)
- **Visit 5:** Speech perception scores will be obtained in Program 2 (Self MAP)

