8 SAMPLE SIZE

Based on the variability observed in earlier studies, it was determined using PASS (NCSS Statistical Software) that a minimum of 26 subjects would provide at least 90% power for hypothesis testing of the two co-primary endpoints at the 0.025 alpha level.

The planned sample size of 40 subjects will provide adequate power for hypothesis testing of the two co-primary endpoints at the 0.025 alpha level. The following general assumptions have been made:

- Paired T-tests of difference scores to test for non-inferiority with a non-inferiority margin of 10% for CNC word recognition
- One-sided 0.025 alpha level
- Assumed distribution for population (standard deviation)
- Desire for 90% power

The power analyses for the primary test metrics are provided below.

Sample size calculation for CNC word recognition:

Scenario (Non-inferiority)	Minimum Evaluable Sample Size Required
One-sided 0.025 alpha, 90% power, SD = 15%, NIM = 10% , true difference = 0	26

More subjects will provide additional power or a similar degree of power for more conservative assumptions. Because the non-inferiority sample size calculation assumes a true difference of 0 between remote and live MAP programming, we propose a sample size of 40 subjects to allow for:

1. the possibility that variability will be greater than expected,
2. the possibility that the true difference may be greater than 0, and
3. the possibility of subject attrition.

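### SAP 11 counts either primary endpoint as study success while each is tested at the full one-sided 0.025, so the stated overall 0.025 is not maintained

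*SAP*

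**What the plan says.** SAP 11 defines study success as rejection of the null for facilitated remote versus live programming "and/or the rejection of the null hypothesis in the comparison of unassisted remote MAP programming via telecommunication to live MAP programming". One rejection is therefore enough. It then makes an error-rate statement about that rule: "Because study success is based on two separate endpoints, type I error will be maintained at an overall one-sided alpha level of 0.025". The only ordering it gives is this: "The secondary efficacy objective will be tested only in the event both co-primary efficacy objectives are met".

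SAP 10.2.1 and 10.2.2 give the same criterion for each primary endpoint: "If the upper limit of the two-sided 95% confidence bound is less than 10, statistical significance will be met at the 0.025 alpha level". SAP 8 and the protocol's Sample Size section use the same unsplit level: "a minimum of 26 subjects would provide at least 90% power for hypothesis testing of the two co-primary endpoints at the 0.025 alpha level". SAP 8 proposes 40 subjects to allow for greater variability, attrition and "the possibility that the true difference may be greater than 0".

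The protocol (Study Summary, Endpoint Testing) calls the two endpoints co-primary but gives no rule for combining them. Both draw on the same live-MAP score: "Efficacy Endpoint 1 testing will occur at Visit 1 and Visit 3" and "Efficacy Endpoint 2 testing will occur at Visit 1 and Visit 5".

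**The concern.** A success rule that either of two tests can satisfy has two chances of a false positive. With each test at 0.025, the overall rate is 0.025 only if the tests are perfectly correlated. SAP 11 recognises that success rests on two endpoints but supplies no alpha split, ordering or step-down procedure between them. The gate on the secondary operates only after both primaries are met, so it cannot protect a claim that needs just one.

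Two things are at stake. The first is an explicit type I error statement about the study-success claim that the decision rule does not deliver. The second is that a trial meeting exactly one endpoint succeeds under *and/or* but fails if co-primary means both. If that is settled after results are known, the choice can be driven by the outcome.

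**Working it through.** **Inputs from the documents.** One-sided 0.025 per test, margin 10, SD 15, true difference 0, 90% power, minimum 26, planned 40 (SAP 8); one-sample t-test on each within-subject difference, live minus remote (SAP 10.2). **Assumed:** the correlation ρ between the two difference scores, which is not given; bivariate normal differences with equal SD.

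**1. The plan's own sample size.** Power is that of a noncentral t with n − 1 degrees of freedom and noncentrality 10√n/15. At 0.025, n = 25 gives 89.2% and n = 26 gives 90.4%. The stated 26 reproduces, for one test at the unsplit level.

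**2. A plausible ρ.** Let the CNC scores at Visits 1, 3 and 5 have common variance σ² and common pairwise correlation r. Each difference from Visit 1 has variance 2σ²(1 − r). Their covariance is σ² − rσ² − rσ² + rσ² = σ²(1 − r). The ratio is 0.5. Without equal variances and correlations ρ may differ, so a range is shown.

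**3. Overall error with both true differences at 10.** P(at least one rejection) = 0.025 + 0.025 − P(both), which is at most 5.0%. If independent, it is 1 − 0.975² = 4.94%. In general the normal form is 1 − Φ₂(1.96, 1.96; ρ). Simulated t-tests (6,000,000 trials per setting) agree:

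| ρ | Bivariate normal | t-tests, n = 40 | t-tests, n = 26 |
|---|---|---|---|
| 0 | 4.94% | 4.95% | 4.93% |
| 0.5 | 4.54% | 4.57% | 4.57% |
| 0.7 | 4.17% | 4.21% | 4.21% |
| 0.9 | 3.52% | 3.54% | 3.55% |
| 0.95 | 3.23% | 3.23% | not run |
| 1 | 2.5% | 2.5% | 2.5% |

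For ρ from 0.9 to 0.5 at n = 40 this is 3.54/2.5 = 1.4 to 4.57/2.5 = 1.8 times the stated rate.

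**4. How often the two readings of the success rule disagree.** Each test at 0.025, SD 15, 2,000,000 trials. Exactly one met = at least one − both.

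| Setting | ρ | At least one | Both | Exactly one |
|---|---|---|---|---|
| n = 40, difference 0 | 0.5 | 99.76% | 97.08% | 2.7% |
| n = 40, difference 0 | 0.9 | 99.14% | 97.74% | 1.4% |
| n = 26, difference 0 | 0.5 | 97.06% | 83.82% | 13.2% |
| n = 26, difference 0 | 0.9 | 93.54% | 87.29% | 6.3% |
| n = 40, difference 2 (assumed) | 0.5 | 97.20% | 84.39% | 12.8% |
| n = 40, difference 2 (assumed) | 0.9 | 93.80% | 87.82% | 6.0% |

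**5. Check of a remedy.** With Holm (first step at 0.0125), the overall error at n = 40 is 2.49%, 2.34%, 2.17% and 1.83% for ρ = 0, 0.5, 0.7 and 0.9.

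**The case against.** The best defence is that *and/or* is a drafting slip. Both documents call the endpoints co-primary. If both must be met, 0.025 per test is correct and nothing is inflated. SAP 11 and 10.3 show other signs of loose drafting: SAP 11 ends in a sentence fragment, and SAP 10.3 calls the secondary a co-primary endpoint. This may explain how the wording arose, but it does not rescue the text. *And/or* is the only explicit success rule in either document, so under this reading the success definition is wrong instead of the alpha statement. SAP 11 needs correcting either way.

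Three limits do stand:

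- The inflation concerns the study-success claim when both remote modes are at or very near the margin. If only one mode is at or beyond it, a false claim for that mode has probability at most 2.5%. The gate also prevents the secondary from adding error.
- The documents alone support only a rate above 2.5% and at most 5%. The 3.5% to 4.6% range depends on an assumed ρ of 0.9 to 0.5.
- In the SAP's planning case with all 40 evaluable, the two readings disagree in under 3% of trials. The 6% to 13% figures need attrition to 26 or an assumed true difference of 2, although SAP 8 itself names attrition and a non-zero difference as possibilities.

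**Conclusion.** The concern holds: SAP 11 is wrong as written and must be fixed. Its either-one rule, with each primary at one-sided 0.025, does not maintain an overall 0.025. With both differences at the margin, false study success is about 3.5% to 4.6% for ρ of 0.9 to 0.5, and 4.9% if independent. The direction needs no assumption beyond ρ below 1; the size depends on ρ. The separate endpoint tests are sound at their own level.

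**What to change.** Adopt one rule in SAP 11 before results are seen:

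- **(a) Keep *and/or*, with Holm.** Test the smaller p-value at one-sided 0.0125 (upper limit of the two-sided 97.5% interval below 10). Test the other at 0.025 only if the first is met, then the secondary at 0.025 if both are met.
- **(b) Fixed sequence at 0.025.** Endpoint 1, then Endpoint 2, then the secondary. Endpoint 1 becomes necessary for success, so the success definition must be rewritten.
- **(c) Replace *and/or* with *and*.** Each primary stays at 0.025.

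Align the confidence level in SAP 10.2, and the sample-size text in SAP 8 and the protocol, with the choice. As an editorial matter, SAP 10.3 should refer to the secondary efficacy endpoint where it now says second co-primary.

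The cost is text only. The planned 40 need not rise at SD 15 and difference 0, but the options differ in power:

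- **(a)** Power per test at 0.0125 against 0.025 is 96.7% against 98.4% at n = 40, and 83.8% against 90.4% at n = 26. At n = 40 it is 84.7% against 90.8% with an assumed difference of 2, and 87.7% against 92.9% with an assumed SD of 18. The minimum for 90% at 0.0125 is 31 (90.5%; n = 30 gives 89.4%). Holm recovers part of the loss: per-endpoint power is 97.7% to 98.2% at n = 40 and 86.9% to 88.4% at n = 26 (ρ 0.9 to 0.5), and 28 to 29 evaluable subjects give 90%.
- **(b)** Endpoint 1 loses nothing, but Endpoint 2 cannot be claimed if Endpoint 1 fails.
- **(c)** Joint power is 97.1% to 97.7% at n = 40 but 83.8% to 87.3% at n = 26 (ρ 0.5 to 0.9; 81.8% if independent). For 90% joint power the stated minimum of 26 would become 29 to 31 evaluable subjects, or 32 if independent.

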12 ADDITIONAL ANALYSES

No formal statistical hypothesis testing will be conducted for the additional endpoints. Statistical comparisons may be presented for descriptive purposes only without adjustment for multiplicity. A nominal $p < 0.05$ will be used to determine statistical significance.

12.1 Subject Disposition

Subject disposition will be presented by:

- Summary of subjects per visit
- Summary of early withdrawal and reason for early withdrawal

12.2 Demographics and Baseline Characteristics

Demographic and baseline characteristics of enrolled subjects will be summarized.

12.3 Within-Subject Differences in CNC test scores

The critical differences (.05 level of confidence) adapted from Thornton and Raffin (1978) will be used for comparison of CNC word recognition scores between each 2 condition comparison. The number of subjects with significantly lower, significantly higher, and similar scores based on the binomial model presented Thornton and Raffin (1978) will be reported for the following comparisons: facilitated remote MAP programming via telecommunication compared to traditional audiologist live MAP programming, unassisted remote MAP programming via telecommunication compared to traditional audiologist live MAP programming, and unassisted remote MAP programming via telecommunication compared to facilitated remote MAP programming via telecommunication.

12.4 Remote Programming Satisfaction Survey

At Visits 2 and 4, the remote programming satisfaction survey will be completed. This survey uses a satisfaction rating scale to gather subjects' opinions regarding the ease, quality, and comfort of the remote programming sessions.

12.5 Speech, Spatial, and Qualities of Hearing Scale (SSQ-C)

At Visits 3 and 5, the SSQ-C will be completed. The SSQ-C will be used as a subject self-assessment in three categories (speech hearing rating scale, spatial rating scale, and sound qualities rating scale). The SSQ-C is the "comparative" version of the SSQ. It can be used for comparing two different hearing

technologies. In this study, the SSQ-C will compare the subject's familiar map (Program #1) and remote MAP (Program #2).

12.6 Telemedicine Experience Questionnaire

At Visit 5, the telemedicine experience questionnaire will be completed. This 5-question survey was specifically designed to examine subjects' evaluations of the telemedicine experience. It includes a response rating scale, as well as the opportunity for open ended feedback.

12.7 Electrical Charge

At Visits 1, 2, and 4, electrical charge information will be collected. Comparisons of T and C levels between MAPs will be conducted using descriptive statistics.

12.8 Exploratory Analyses

Additional, ad hoc exploratory analyses may also be conducted.

12.9 Other Data

Protocol deviations will be listed and tabulated.

13 POOLING ACROSS SITES

Pooling data from study sites will be justified based on the following: all sites will have the same protocol, the sponsor will monitor the sites to assure protocol compliance, and the data gathering mechanism (case report forms and data acquisition) will be the same across all study sites.

Consistency of the primary efficacy endpoints will be assessed by testing for a difference between sites in the difference between facilitated remote MAP programming via telecommunication and live MAP programming for CNC word recognition and by testing for difference between sites in the difference between unassisted remote MAP programming via telecommunication and live MAP programming for CNC word recognition. Testing will be conducted via an analysis of variance model, with difference between testing conditions as the outcome and site as the factor. A p-value for the site factor of less than 0.15 will be considered evidence of differences between sites for one of the primary efficacy endpoints. If there is evidence of a difference, additional analyses will be performed to explore the possible role of baseline characteristics to explain the results. Results for the primary efficacy endpoint will also be presented separately by site, irrespective of the test of differences between sites, to help understand both qualitative and non-significant differences between sites

14 MISSING DATA

All efforts will be put forth to ensure near complete follow-up, with particular focus on the assessment of the primary outcomes and occurrence of adverse events. A reminder of subject follow-up due dates will be provided to participating centers to facilitate scheduling of the follow-up visits.

Sensitivity analysis will be conducted to address the potential impact of missing endpoint data using a multiple imputation analysis with 10 imputed datasets. Missing data for CNC score under each condition will be imputed. The imputed datasets will then be combined for inference using standard methods such as those available in SAS PROC MIANALYZE or other valid statistical software. In addition, comparisons of baseline characteristics between those with missing data and those without will be conducted. This will provide an assessment as to whether there are systemic differences in subjects who miss visits.

16 VERSION HISTORY

Version	Date	Changes
1.0	27Oct2015	
1.1	04Dec2015	Added section 12.7 Electrical charge. Added additional detail to section 14: Missing data (second paragraph regarding multiple imputation).
